#### 3.2 Secondary Objective(s) & Hypotheses

(1) **Objective:** To characterize freedom from distant metastasis rates following treatment with sequential pembrolizumab and radiotherapy for locally advanced NSCLC with PD-L1 expression  $\geq 50\%$ .

**Hypothesis:** We hypothesize that sequential pembrolizumab and radiotherapy for locally advanced NSCLC with PD-L1 expression  $\geq 50\%$  prolongs freedom from distant metastasis compared to historical outcomes.

(2) **Objective:** To characterize freedom from intrathoracic disease progression rates following treatment with sequential pembrolizumab and radiotherapy for locally advanced NSCLC with PD-L1 expression  $\geq 50\%$ .

**Hypothesis:** We hypothesize that sequential pembrolizumab and radiotherapy for locally advanced NSCLC with PD-L1 expression  $\geq 50\%$  prolongs freedom from intrathoracic disease progression compared to historical outcomes.

(3) **Objective:** To characterize overall survival rates following treatment with sequential pembrolizumab and radiotherapy for locally advanced NSCLC with PD-L1 expression  $\geq 50\%$ .

**Hypothesis:** We hypothesize that sequential pembrolizumab and radiotherapy for locally advanced NSCLC with PD-L1 expression  $\geq 50\%$  prolongs overall survival compared to historical outcomes.

(4) **Objective:** To estimate the rate of disease progression during 3 cycles of induction pembrolizumab prior to radiotherapy for locally advanced NSCLC with PD-L1 expression  $\geq 50\%$ .

**Hypothesis:** We hypothesize that the rate of disease progression during 3 cycles of induction pembrolizumab prior to radiotherapy for locally advanced NSCLC with PD-L1 expression  $\geq 50\%$  is less than 10%.

(5) **Objective:** To demonstrate, within the limitations of a nonrandomized study, that sequential pembrolizumab and radiotherapy for locally advanced NSCLC reduces severe adverse event rates compared to standard concurrent chemoradiotherapy.

**Hypothesis:** We hypothesize that sequential pembrolizumab and radiotherapy for locally advanced NSCLC reduces severe adverse event rates compared to standard concurrent chemoradiotherapy.

(6) **Objective:** To demonstrate, within the limitations of a nonrandomized study, that sequential pembrolizumab and radiotherapy for locally advanced NSCLC does not significantly increase rates of pneumonitis compared to standard concurrent chemoradiotherapy.

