#### **4.6.2.2 Safety Endpoints**

- Severe (grade  $\geq 3$ ) adverse events, scored using CTCAE v 4.03.
  - It will be important to characterize the toxicity profile of sequential pembrolizumab and radiotherapy for locally advanced NSCLC, as this is a novel treatment approach.
- Pneumonitis (grade  $\geq 2$ ).
  - It will be important to characterize the rate of pneumonitis, which may occur because of radiotherapy or immunotherapy, for study subjects.
- Patient-reported treatment-related toxicity, scored using PRO-CTCAE.
  - See Section 4.5
- Unplanned hospitalization.
  - Many patients treated with radiotherapy or chemoradiotherapy for locally advanced NSCLC are hospitalized due to treatment toxicity. It will be important to characterize the hospitalization rate for patients treated with pembrolizumab and radiotherapy for locally advanced NSCLC.
- Daily step counts, measured using wearable fitness trackers.
  - See Section 4.4

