## 5.2 Study Treatments and Activity Monitoring

### 5.2.1 Pembrolizumab (PembroRT Cohort Only)

#### 5.2.1.1 Pembrolizumab Timing

The timing of pembrolizumab infusions is summarized in the Study Flow Chart. Trial treatment may be administered up to 3 days before or after the scheduled treatment due to administrative reasons. Trial treatments should be administered on an outpatient basis.

Pembrolizumab 200 mg will be administered as a 30-minute IV infusion every 3 weeks. Sites should make every effort to target infusion timing to be as close to 30 minutes as possible. Given the variability of infusion pumps from site to site, a window of -5 minutes and +10 minutes is permitted (i.e., infusion time is 30 minutes: -5 min/+10 min).

The Pharmacy Manual contains specific instructions for the preparation of the pembrolizumab infusion fluid and administration of infusion solution.

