#### **5.2.2 Chemotherapy (ChemoRT Cohort Only)**

Chemotherapy will be administered weekly during radiotherapy. This concurrent chemotherapy will consist of carboplatin (AUC 2, IV) and paclitaxel (50 mg/m^2, IV). Standard institutional procedures will be used for chemotherapy formulation, calculation of AUC, and chemotherapy administration. Treating physicians may implement dose reductions or withhold chemotherapy in the event of adverse events or laboratory abnormalities, per usual care.

Adjuvant systemic therapy may be administered for patients on the ChemoRT cohort, at the discretion of the treating physicians. In some cases, this may consist of adjuvant systemic doses of chemotherapy (e.g.: carboplatin AUC 6 and paclitaxel 200 mg/m^2). Based on emerging data[10], patients on the ChemoRT cohort may be treated with adjuvant immunotherapy.

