## 6.0 TRIAL FLOW CHART

PD-L1 ≥ 50%: PembroRT	Eval Week:	Induction Pembrolizumab									Radiotherapy							Maintenance Pembrolizumab													
		1	2	3	4	5	6	7	8	9	10	11	12	13	14	15	16	17	18	21	24	27	30	33	36	39	42	45	48	51	
History, Physical, Toxicity Assessment	X	X			X			X			X	X	X	X	X	X	X	X	X	X	X	X	X	X	X	X	X	X	X		
PRO-CTCAE Assessment	X	X			X			X			X	X	X	X	X	X	X	X	X	X	X	X	X	X	X	X	X	X	X		
PET/CT	X																														
CT C/A																															
Biopsy, Tumor PD-L1 Testing	X																														
Serum Correlative Studies	X																														
Pembrolizumab																															
Dose-Painted Radiotherapy																															
PD-L1 < 50%: ChemoRT	Eval Week:	Chemoradiotherapy										Optional Adjuvant Therapy, Observation																			
		1	2	3	4	5	6	7	8	9	10	11	12	13	14	15	16	17	18	21	24	27	30	33	36	39	42	45	48	51	
History, Physical, Toxicity Assessment	X	X	X	X	X	X	X	X	X	X	X+																				
PRO-CTCAE Assessment	X	X		X		X		X		X	X+																				
PET/CT	X																														
CT C/A																															
Biopsy, Tumor PD-L1 Testing	X																														
Serum Correlative Studies	X																														
Carboplatin/Paclitaxel																															
Radiotherapy																															
		XXXXX	XXXXX	XXXXX	XXXXX	(XXXXX)	(XXXXX)	(XXXXX)	(XXXXX)	(XXXXX)		(X*)							(X*)												

( ) - Optional

^ - May be replaced by PET/CT

\* - Every 3 weeks, starting 4-6 weeks after completion of radiotherapy

+ - May be performed one week before or after the protocol-specified timepoint

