### 8.2 Statistical Analysis Plan – Secondary Endpoints

Time-to-event outcomes (overall survival, freedom from distant metastasis, freedom from intrathoracic progression, freedom from hospitalization) will be analyzed using the Kaplan-Meier method, from which rates at various time points and corresponding 95% confidence intervals will be estimated. Exploratory comparisons for time-to-event outcomes between the PembroRT and ChemoRT cohorts will be performed using log-rank tests. Univariate and

multivariable Cox regression models will be used to evaluate associations between time-to-event outcomes and clinical covariates, including study cohort.

Rates of radiographic responses and disease progression during induction pembrolizumab for subjects in the PembroRT cohort will be described using counts and percentages. Logistic regression models will be used to evaluate potential predictors of response or progression (e.g.: PD-L1 TPS).

Hospitalization rates and adverse event rates, scored using CTCAE as well as PRO-CTCAE, will be presented as counts and percentages. Exploratory comparisons between the PembroRT cohort and the ChemoRT cohort will be performed using chi-square or Fisher Exact testing, as appropriate.

Daily step counts throughout the study period will be presented using descriptive statistics and will be analyzed using a generalized linear mixed-model for repeated measures.

Rates of circulating tumor DNA clearance will be presented as counts and percentages, and predictors of circulating tumor DNA clearance will be explored using chi-square or Fisher exact testing, as appropriate. Exploratory analyses will be performed to evaluate PD-L1 expression, expression of alternative immune checkpoint molecules (e.g., HHLA2, B7x, and B7-H3), baseline tumor mutational burden, and markers of immune activation (e.g., expansion of T4/T8 subsets, myeloid derived suppressor cell levels, expansion of T-cell repertoire) as predictors of PFS and overall survival.

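### Section 8.2 compares crude grade ≥3 adverse event and grade ≥2 pneumonitis percentages between cohorts with no common observation period, and the length of ChemoRT observation turns on an unstated classification of adjuvant therapy

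*Combined protocol and SAP*

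**What the plan says.** Secondary objective 5 (section 3.2) is to demonstrate fewer severe AEs than with chemoradiotherapy. Objective 6 is to demonstrate that PembroRT "does not significantly increase rates of pneumonitis compared to standard concurrent chemoradiotherapy". Section 4.6.2.2 defines the endpoints as grade ≥3 AEs and grade ≥2 pneumonitis, and describes pneumonitis as an event "which may occur because of radiotherapy or immunotherapy, for study subjects". Neither endpoint has a time window.

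Section 8.2 states: "Hospitalization rates and adverse event rates, scored using CTCAE as well as PRO-CTCAE, will be presented as counts and percentages". Cohorts are compared by chi-square or Fisher's exact test, labelled exploratory. Hospitalization also gets a time-to-event analysis in the same section ("freedom from hospitalization) will be analyzed using the Kaplan-Meier method"). AEs and pneumonitis do not.

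The AE collection rules are:

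- Section 5.7: to 90 days after the last study treatment. A second sentence ends collection earlier if another anti-cancer therapy starts.
- Section 7.1.5.1: all AEs to a visit about 30 days after the last dose, or before new therapy if sooner; serious AEs to 90 days or new therapy.
- Section 7.2: all AEs to 30 days, with no cut for new therapy; serious AEs to 90 days, or 30 if new therapy starts.
- Section 7.1.2.1: throughout the study and follow-up.

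For ChemoRT, section 5.2.2 adds: "Adjuvant systemic therapy may be administered for patients on the ChemoRT cohort, at the discretion of the treating physicians". This may include immunotherapy. The flow chart heads the later ChemoRT weeks "Optional Adjuvant Therapy, Observation" and times the optional therapy as "Every 3 weeks, starting 4-6 weeks after completion of radiotherapy".

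**The concern.** A crude percentage is the proportion of patients with an event while someone was recording events. It compares two cohorts fairly only if they are observed for similar lengths of time. Three of the four collection rules are anchored to the last study treatment. That is about one year for PembroRT (15 doses, section 5.5) but 20–37 radiotherapy fractions for ChemoRT (section 5.2.3), unless adjuvant therapy extends it.

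If ChemoRT observation is short, later ChemoRT events are missed while PembroRT events are recorded through maintenance. A real reduction in severe AEs (objective 5) could then be masked, and a pneumonitis excess (objective 6) could appear where none exists. Pneumonitis is exposed because the protocol expects it from either radiotherapy or immunotherapy, so events well after radiotherapy matter in both cohorts.

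**Working it through.** **Plan's own figures.** The plan gives no expected AE rates and no power for these comparisons, so there is no AE figure to reproduce. The cohort sizes follow from section 8.1: 25 PembroRT, and 25/0.40 × 0.60 = 37.5, about 38 ChemoRT.

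**Observation windows.** I assume five fractions a week, so ChemoRT radiotherapy lasts 20/5 = 4 to 37/5 = 7.4 weeks. I assume the last pembrolizumab dose is at week 51, the last flow-chart column. Thirty days is 4.3 weeks and 90 days is 12.9.

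| Rule, adjuvant not counted | PembroRT (weeks) | ChemoRT (weeks) | Ratio |
|---|---|---|---|
| 30 days | 51 + 4.3 = 55.3 | 8.3–11.7 | 4.7–6.7 |
| 90 days | 51 + 12.9 = 63.9 | 16.9–20.3 | 3.2–3.8 |

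If adjuvant therapy counts and lasts 52 weeks (assumed; section 4.6 mentions one year of adjuvant durvalumab), starting 4–6 weeks after radiotherapy, ChemoRT is observed for 64.3–69.7 weeks (30 days) or 72.9–78.3 weeks (90 days). The ratio is then 0.79–0.88.

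**Effect on the test.** Assume equal true risk, a 20% ChemoRT rate in its 90-day window c, all 15 doses given, and no adjuvant therapy counted. Then h = −ln(0.80)/c. If the hazard after c is f × h and the PembroRT window is p, the PembroRT percentage is 1 − exp{−h[c + f(p − c)]}. For c = 16.9, p = 63.9 and f = 1 this is 1 − 0.80^3.79 = 57%. Exact enumeration of the two-sided 5% Fisher test, 25 v 38, gives:

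| Later hazard | PembroRT percentage | Significant false PembroRT excess |
|---|---|---|
| Common window | 20% | 2.3% |
| One tenth | 24–25% | 4.8–5.8% |
| One quarter | 29–32% | 11–16% |
| Constant (upper bound) | 51–57% | 68–84% |

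If PembroRT patients stop at progression (exponential, 65% one-year PFS), the last three rows become 4.0–4.9%, 8–12% and 50–67%.

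**Masking.** With a truly halved hazard, 1 − exp{−0.5h[c + f(p − c)]}, PembroRT would show 11% against 20% over equal time. Over the unequal windows it shows 13%, 16–17% or 30–34% for the three later hazards.

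**If adjuvant therapy counts.** At 50% uptake, with both cohorts stopping at progression, the false-excess figures are 2–3%, 3–5% and 8–19%. At 100% uptake a false PembroRT excess has probability 0.4–2.1% and a false ChemoRT excess 1.5–7%. Without stopping, average windows are equal at uptake (p − c)/(c_adj − c), where c_adj is the ChemoRT window with adjuvant therapy counted. For example, (63.9 − 16.9)/(72.9 − 16.9) = 0.84; the range is 0.75–0.84.

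**The case against.** The strongest reply is that adjuvant therapy is best read as protocol treatment. It is described under "5.2 Study Treatments and Activity Monitoring". Section 5.4.2 prohibits only chemotherapy and immunotherapy that the protocol does not specify. The flow chart gives the adjuvant therapy its own timing. Section 4.6 says consolidation immunotherapy has become standard for many such patients, so negligible uptake is not the natural base case. This largely stands, and it shrinks the problem. It does not close it, because no section states the classification for AE collection and uptake is left to physicians.

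A reader might infer that section 5.7 closes ChemoRT collection once adjuvant therapy starts, at week 8–13.4, giving a ratio of 4.8–8.0. That requires adjuvant therapy to be another anti-cancer therapy, which the sections just cited make the least supported reading.

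A reader might also infer that ChemoRT patients have no toxicity assessment after chemoradiotherapy. The documents do not support that either. The flow-chart rows are broken in the available text, so later visits cannot be excluded, and section 7.1.2.1 records AEs through follow-up. That section still conflicts with section 5.7 and sets no analysis window.

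Finally, the comparison is exploratory, nonrandomized and confounded by PD-L1 allocation. That limits its importance, but those caveats concern comparability of patients. They do not warn of unequal observation time, which, unlike confounding, can be removed.

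**Conclusion.** The concern holds in a limited form. Section 8.2 compares percentages with no common period, and the collection rules do not supply one. The direction and size of the resulting bias depend on two things the plan leaves open: how ChemoRT adjuvant therapy is classed, and how many patients receive it. The bias runs against PembroRT if adjuvant therapy is uncounted or uncommon, and is small or reversed if it is counted and nearly universal. It would be wrong to conclude that the plan is certainly biased against PembroRT.

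The probabilities are illustrative. They rest on an assumed 20% rate, assumed hazard shapes, five fractions a week and a last dose at week 51. The 68–84% figure needs a constant hazard and is an upper bound; with a low later hazard the effect is modest. The primary endpoint is unaffected. This is a cheap improvement to a secondary analysis.

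**What to change.** 1. Reconcile sections 5.7, 7.1.2.1, 7.1.5.1 and 7.2 into one AE collection period that runs to the same time from registration in both cohorts, and state how ChemoRT adjuvant therapy is classed.
2. In section 8.2, replace the crude-percentage comparison of grade ≥3 AEs and grade ≥2 pneumonitis with cumulative incidence at that time, for example 12 months, with death as a competing event. If collection stops at progression, treat progression as a competing event in both cohorts too.
3. Add a supportive pneumonitis analysis over equal time from the start of radiotherapy, noting that it omits induction toxicity.

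Twelve months suits pneumonitis better than six. Assuming PembroRT radiotherapy ends at week 13–16, six months (26.1 weeks) from registration leaves 10–13 weeks after radiotherapy for PembroRT but 19–22 for ChemoRT. Twelve months (52.2 weeks) leaves 36–39 and 45–48.

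**Cost.** Besides wording, ChemoRT AE recording must extend to the common time. The 12-weekly contacts in sections 7.1.5.2 and 7.1.5.3 now cover only imaging and survival status, so a toxicity question must be added at every site. If that is not accepted, restrict the comparison to the longest period from registration that is collected in both cohorts. That fallback is weaker: with adjuvant therapy uncounted, the period could be as short as 8.3 weeks (30-day rule) or 16.9 weeks (90-day rule), so little or no post-radiotherapy time would be compared for PembroRT.

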**Hypothesis:** We hypothesize that sequential pembrolizumab and radiotherapy for locally advanced NSCLC not significantly increase rates of pneumonitis compared to standard concurrent chemoradiotherapy.

(7) **Objective:** To demonstrate, within the limitations of a nonrandomized study, that sequential pembrolizumab and radiotherapy for locally advanced NSCLC reduces patient-reported treatment-related toxicities compared to standard concurrent chemoradiotherapy.

**Hypothesis:** We hypothesize that sequential pembrolizumab and radiotherapy for locally advanced NSCLC reduces patient-reported treatment-related toxicities compared to standard concurrent chemoradiotherapy.

(8) **Objective:** To demonstrate, within the limitations of a nonrandomized study, that sequential pembrolizumab and radiotherapy for locally advanced NSCLC preserves physical function compared to standard concurrent chemoradiotherapy.

**Hypothesis:** We hypothesize that sequential pembrolizumab and radiotherapy for locally advanced NSCLC preserves physical function, as measured by daily step counts, compared to standard concurrent chemoradiotherapy.

(9) **Objective:** To demonstrate, within the limitations of a nonrandomized study, that sequential pembrolizumab and radiotherapy for locally advanced NSCLC reduces hospitalization rates compared to standard concurrent chemoradiotherapy.

**Hypothesis:** We hypothesize that sequential pembrolizumab and radiotherapy for locally advanced NSCLC reduces hospitalization rates compared to standard concurrent chemoradiotherapy.

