#### 4.5 Patient-Reported Outcomes

Patient-reported outcomes are becoming a standard tool for evaluating health-related quality of life, treatment preferences, and treatment quality in cancer care[35]. They may be particularly important in studies involving radiotherapy for NSCLC. This is exemplified by the results of RTOG 0617, which was a multi-institutional randomized trial testing uniform radiotherapy dose escalation (including all tumors and regional lymph nodes) with concurrent chemotherapy for LA-NSCLC. Dose escalation from 60 Gy to 74 Gy was unexpectedly found to increase the risk of mortality, with median overall survival durations of 29 months with the standard dose of 60 Gy and only 20 months for subjects treated with 74 Gy[17]. Investigators found no statistically significant differences in serious (grade  $\geq 3$ ) adverse events between radiotherapy dose groups, demonstrating the disconnect between physician-scored toxicity and important clinical outcomes. Impairments in patient-reported quality of life, on the other hand, occurred more frequently in the high dose radiotherapy arm[36]. Additionally, baseline quality of life score was found to be a powerful predictor of overall survival.

The National Cancer Institute recently developed the Patient-Reported Outcomes Version of the Common Terminology Criteria for Adverse Events (PRO-CTCAE)[37]. The PRO-CTCAE item library is comprised of 78 symptomatic adverse events, each of which is elicited using between one and three questions (representing frequency, severity, and/or interference), for a total of 124 individual questions. For any given clinical trial, relevant PRO-CTCAE items can be selected from the online library to create a concise patient questionnaire that has been validated in several languages. This promising tool has not yet been utilized extensively in chemoradiotherapy trials for NSCLC. One recent study demonstrated the extent to which CTCAE and PRO-CTCAE findings may differ in this setting[38]. As an example, clinicians using CTCAE reported that high-level anxiety occurred in 0/130 subjects. PRO-CTCAE demonstrated that 28/120 subjects

had high-level anxiety. Large differences between CTCAE and PRO-CTCAE were observed for several other adverse events, including anorexia, cough, dysphagia, fatigue, and pain.

[figure not shown]

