### 5.3 Treatment Allocation

Subjects will be stratified based on baseline PD-L1 TPS score. Subjects whose score is less than 50% will be treated with chemotherapy and radiotherapy (ChemoRT Cohort). Subjects whose score is 50% or higher will be treated with pembrolizumab and radiotherapy (PembroRT Cohort).

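### Section 8.2 compares PRO-CTCAE rates between the PD-L1-allocated cohorts without adjustment and specifies no use of the evaluation-visit PRO-CTCAE score

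*Combined protocol and SAP*

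**What the plan says.** - **Summary and test.** Section 8.2 says that "adverse event rates, scored using CTCAE as well as PRO-CTCAE, will be presented as counts and percentages". It continues: "Exploratory comparisons between the PembroRT cohort and the ChemoRT cohort will be performed using chi-square or Fisher Exact testing, as appropriate". For PRO-CTCAE it gives no event threshold, time window, baseline rule or covariate.
- **Other outcomes in the same section.** For time-to-event outcomes, "multivariable Cox regression models will be used to evaluate associations between time-to-event outcomes and clinical covariates, including study cohort". Daily step counts get a repeated-measures mixed model. Neither approach is extended to PRO-CTCAE.
- **What the comparison serves.** Objective 7 in section 3.2 is to show, within the limits of a nonrandomized study, that the experimental regimen "reduces patient-reported treatment-related toxicities compared to standard concurrent chemoradiotherapy". Section 4.6.2.2 lists the endpoint as "Patient-reported treatment-related toxicity, scored using PRO-CTCAE".
- **Allocation.** Under section 5.3 the cohort is set by PD-L1 score at a 50% cutoff.
- **Baseline form.** The "PRO-CTCAE Assessment" row of the flow chart (section 6.0) is marked in the evaluation column for both cohorts. The chart is partly damaged in the text available, but these two entries are readable. Nothing below relies on the number of later forms.
- **Instrument.** The items in Appendix 5 ask how often a symptom occurred, how severe it was or how much it interfered over the past seven days. They do not ask for its cause.

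**The concern.** Cough, breathlessness, fatigue and anxiety can be present in lung cancer patients before any treatment. A count of patients reporting such a symptom after treatment starts therefore mixes pre-existing symptoms with toxicity, unless the count or the test refers back to baseline. Without randomization, nothing in the design balances baseline symptoms between the cohorts. A difference could then look like a toxicity benefit that does not exist, or hide one that does.

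The protocol supplies the means to separate the two, because the form is scheduled before treatment in both cohorts. Its own background also treats baseline patient reports as informative: in an earlier radiotherapy trial "baseline quality of life score was found to be a powerful predictor of overall survival" (section 4.5). That remark concerns survival. It does not show that symptoms differ by PD-L1 group.

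At stake is how objective 7 is interpreted. The primary endpoint and the sample size are unaffected.

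**Working it through.** **Inputs from the plan (section 8.1).** 25 PembroRT patients and an expected 40% with PD-L1 of at least 50%. Total = 25 / 0.40 = 62.5, rounded up to 63; ChemoRT = 63 − 25 = 38. The stated sizes reproduce. The plan gives no operating figure for the PRO-CTCAE comparison, so there is none to reproduce.

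**Assumed inputs.** The documents give no symptom prevalence. I assume a baseline prevalence b in each cohort, a probability t = 0.30 of new toxicity in both cohorts (no treatment effect), and a two-sided 5% test.

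**Reading A: pre-existing symptoms count and persist.** The event rate is 1 − (1 − b)(1 − t).

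For b = 20% vs 35%: 1 − 0.80 × 0.70 = 0.440 and 1 − 0.65 × 0.70 = 0.545. Fisher and uncorrected chi-square are by full enumeration at 25 vs 38. The Mantel-Haenszel test, stratified by baseline, is from 40,000 simulated trials.

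| Baseline, PembroRT vs ChemoRT | Event rates | Fisher | Chi-square | Stratified |
|---|---|---|---|---|
| 25% vs 30% | 0.475 vs 0.510 | 4.6% | 5.9% | 5.0% |
| 25% vs 35% | 0.475 vs 0.545 | 6.9% | 8.5% | 4.9% |
| 20% vs 35% | 0.440 vs 0.545 | 10.7% | 12.9% | 5.0% |
| 20% vs 40% | 0.440 vs 0.580 | 16.5% | 19.4% | 4.9% |

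If 20% or 40% of baseline symptoms resolve, Fisher's 10.7% falls to 8.1% or 5.8%.

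**Reading B: only new or worse symptoms count.**
- Patients free of the symptom at baseline, 30% vs 30%: Fisher 3.4% (enumerated at the full 25 vs 38).
- All patients in the denominator, b = 20% vs 35%: 0.80 × 0.30 = 0.240 vs 0.65 × 0.30 = 0.195. Fisher gives 6.1% and chi-square 7.3%.

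**Power, with assumed new toxicity 20% vs 45%.**
- Equal 30% baselines, reading A: event rates 1 − 0.70 × 0.80 = 0.440 vs 1 − 0.70 × 0.55 = 0.615. Chi-square has about 28% power and the stratified test about 40%.
- Equal 30% baselines, reading B: 0.70 × 0.20 = 0.140 vs 0.70 × 0.45 = 0.315. Chi-square has 37.6%, against 39.7% stratified.
- Baseline 35% vs 20%, reading A: chi-square detects the benefit about 9.5% of the time, the stratified test 39%. Under reading B, plain chi-square among patients free of the symptom at baseline has 40.0%.

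So most of the gain comes from referring the event to baseline. Stratifying adds little power after that, but it holds the level near 5% when baselines differ.

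**The case against.** The strongest reply is that the protocol already points to reading B. Section 7.1.2.1 has participants assessed for new or worsening adverse events. Section 7.2 counts the worsening of a pre-existing condition as an adverse event, and section 8.2 calls the PRO-CTCAE quantities adverse event rates. On that reading the evaluation score is used implicitly, and there is little inflation or loss of power. This stands in part: it is the only event concept in the documents. But neither section mentions PRO-CTCAE, the questionnaire records a symptom level and not a change, and section 8.2 defines no event. The reading is plausible but unstated.

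Second, the comparison is labelled exploratory and objective 7 carries its own caveat about nonrandomized data. That stands, and it limits the severity. A caveat does not, however, remove a bias that data already scheduled can reduce.

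Third, there is no evidence of imbalance. That also stands. Both cohorts share the ECOG 0-1 requirement, and section 4.6 reports no association of PD-L1 with hospitalization or step counts. Those data do not cover symptoms, so they do not settle the question either way.

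A reader might infer that the plan rules out using the baseline score. It does not: it is silent.

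**Conclusion.** A minor point that holds. Section 8.2 specifies an unadjusted comparison and assigns no use to a baseline score collected in both cohorts, although the objective concerns treatment-related toxicity.

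The size depends on two things that the documents do not settle: whether unchanged pre-existing symptoms count as events, and whether baseline symptoms differ between cohorts. If they count and the assumed gap is 15 points with full persistence, the false-positive rate is 10.7% (Fisher) or 12.9% (chi-square), against about 5% stratified. With a 5-point gap there is no material inflation. If only new or worse symptoms count, Fisher gives 3.4% to 6.1% and the power gain from stratifying is small.

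A reader might take 10.7% as the error rate of this plan, or conclude that the PRO-CTCAE results will be biased. The documents support neither: every prevalence here is assumed, and no section shows an imbalance.

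**What to change.** In section 8.2, for PRO-CTCAE only, add:

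> For each item, an event is a post-baseline score worse than the evaluation-visit score. The cohorts will be compared by a Mantel-Haenszel test stratified by the evaluation-visit score level, over an assessment period comparable in both cohorts and fixed before analysis. Items with essentially no baseline variation (e.g. radiation skin burns) keep the chi-square or Fisher test. These comparisons are exploratory.

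Naming one method is deliberate. At this sample size the stratified test held its level (4.7% to 5.1%) in the simulations, while an ordinal logistic model with the baseline score as covariate rejected at 6.1% to 6.7% when baselines differed. The skin-burn exception follows from section 5.1.2, which lists prior thoracic radiotherapy as a contraindication.

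The cost is analysis text and programming, with no new forms or visits. Patients without an evaluation form drop out of the comparison. With 15% missing at random, the level stays at 4.9%, and power in the 35% vs 20% case falls from 39% to 33%. Induction puts the evaluation score further from the radiotherapy-period forms in PembroRT, so adjustment may be weaker there. Other confounding by PD-L1 group remains.
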